#### Accuracy

For people with Mild AD dementia or MCI due to AD reference ranges are available from research cohorts and P-tau 181 alone has an Area Under Receiver Operating Characteristic curve (AUROC) of 0.80 compared to amyloid PET [23] and the combination of NFL and P-tau 181 has an AUROC of 0.88 compared to delayed verification of AD (sensitivity 83-88%, specificity 82-83%) to identify people who have progressive AD pathology as a cause of their MCI at baseline. Simple cognitive tests carried out in clinic such as the Montreal Cognitive Assessment have 90% and 100% sensitivity for MCI and mild AD dementia respectively, with specificity varying according to the cohort (up to 87% when comparing to healthy control in a research cohort) [24]. For people without AD – cerebrospinal fluid (CSF) biomarkers have a very high negative predictive value (94% on a real-world sample after median 4.7 years follow-up). Modelling suggests that combining blood biomarkers with simple cognitive tests will be more sensitive and specific than either test alone.

SleepAD Protocol v6.0 6th September 2024

As blood biomarkers make large scale interventional studies possible in AD at vastly reduced expense (as we can avoid CSF testing or PET scanning), new therapeutic targets for intervention can be tested more rapidly.

The value of blood biomarkers is ultimately determined by the accuracy with which they can predict future AD, and therefore collecting longitudinal data is essential, with progression from MCI to AD as the key outcome of interest. To this end, our pre-clinical/MCI cohort will be followed up at 2 and 5 years after their involvement in the study, to check whether their diagnosis has converted to AD or another dementia. Diagnostic accuracies of all included biomarkers will be assessed, and we will use modelling to examine how specific biomarkers improve dementia risk prediction when combined with baseline demographic and clinical information.

Molecular classification of AD is important alongside exploration of sleep as several studies have suggested distinct interaction between different underlying AD pathology (amyloid, tau or other) and different sleep metrics e.g. [17, 25]. Only by deep characterisation of sleep phenotype as in SleepAD, can we develop clinical trials that target the right sleep treatment to the right patient.

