#### **4 STUDY POPULATION**

#### 4.1 Method Of Recruitment

#### Sub-Study 1

Target population and inclusion/exclusion criteria: The primary method of recruitment will be to approach participants who fulfil the criteria of Mild Cognitive Impairment (MCI) or early dementia due to Alzheimer's Disease (AD) [51] in the ARUK funded DOPAMIND 2 trial (set to begin recruitment November 2022) and the Above and Beyond Funded RESTED study (recruiting from November 2021). Both studies are run by our research group and participants have consented to being approached about other research opportunities.

If we do not meet the sample size from these two studies, participants will be identified by the research team through one of six sources:

- 1. The North Bristol NHS Trust Cognitive Disorders Clinic (led by EC) which receives approximately 20-25 referrals on a weekly basis.
- 2. The North Bristol NHS Trust Mild Cognitive Impairment Clinic / Brain Health Clinic which currently holds a caseload of approximately 80.
- 3. Memory Clinic Database A confidential and secure database maintained by the ReMemBr group in North Bristol NHS Trust for the purposes of undertaking medical research and statistical analysis currently holding approximately 1600 records. This contains contact details for current and previous CDC or MCI clinic attendees, a proportion of whom have previously expressed an interest in future research participation.
- 4. In addition we will recruit through the Join Dementia Research (JDR) national research register for local people interested in taking part. If clinical research network portfolio status is granted, we will recruit with support of local clinical research network staff where appropriate.
- 5. Participants in other research studies (beyond those already stated above) run at the Bristol Brain Centre, who meet eligibility criteria.
- 6. Members of the public who have approached the Brain Centre expressing interest in research participation.

We plan to recruit through primary care and from public spaces using posters and leaflets where we may reach potential participants e.g. hospital and GP waiting rooms. We will advertise this study on our website at www.remembrgroup.com and possibly on other websites.

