#### Follow-up checks of medical records

Medical records from participants in both substudies will be checked again at 2 years and at 5 years after involvement in the study. This will only include available records from those participants in the pre-clinical/MCI phase at time of participation in the study. In both substudies, the date will be measured from the date of the last participant's venepuncture. This follow-up data will be extracted to identify whether the pre-clinical / MCI diagnosis has changed to a dementia diagnosis.

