#### Data analysis will:

- a) Quantify the proportion of lost/degraded blood samples, and data completeness for memory tests
- b) Calculate diagnostic accuracy of the separate index tests (NFL, p-tau) for AD, at prepublished thresholds, compared to reference standard (CSF), via AUROC curves[65]
  - and explore heterogeneity in diagnostic accuracy of index tests AD by prespecified factors listed using cut offs for AD | no AD extrapolated from UCL clinical laboratories.
- Quantify the relationship between p-tau, NFL and sleep metrics in patients who have had both blood biomarkers and high-density EEG
- d) As a post hoc analysis, we will explore the diagnostic accuracy of Montreal Cognitive Assessment (MoCA) as a standard clinical test and visually compare accuracy of NFL and tau to that of MoCA.
- e) Where CSF is available, we will run biomarker analyses on the UCL research SIMOA machine to internally validate samples also tested as part of routine clinical care on the UCL clinical laboratory SIMOA machine.
- f) Once longitudinal data has been collected from our pre-clinical/MCI cohort, we will calculate the diagnostic accuracy of the separate index tests for AD via AUROC curves. The relationship between conversion to AD and the index tests will be assessed using regression models with age, sex, baseline MoCA score, plasma: CSF orexin ratio, and baseline APOE carrier status as covariables.

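### The 2- and 5-year record check cannot tell a participant reviewed and still free of dementia from one whose record stopped early or who died, so unrecognised converters can enter the controls of the progression AUROC

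*Protocol*

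**What the plan says.** Section 8.2 of the protocol, under the follow-up checks of medical records, sets the source and timing: "Medical records from participants in both substudies will be checked again at 2 years and at 5 years after involvement in the study". It restricts who is covered: "This will only include available records from those participants in the pre-clinical/MCI phase at time of participation in the study". It then gives the purpose of the extraction: "This follow-up data will be extracted to identify whether the pre-clinical / MCI diagnosis has changed to a dementia diagnosis". The word available is not defined. No section plans a visit, call or reassessment at these times, and none asks for the date of the last diagnostic review, the date of death, or a category for participants whose status cannot be judged.

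Section 10.2, Substudy 2, item f) uses the result twice. For the pre-clinical/MCI cohort, "we will calculate the diagnostic accuracy of the separate index tests for AD via AUROC curves", and "The relationship between conversion to AD and the index tests will be assessed using regression models". The Accuracy part of the Background explains why this matters: "collecting longitudinal data is essential, with progression from MCI to AD as the key outcome of interest".

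**The concern.** Under a passive check, a conversion is seen only if somebody reassessed the participant and recorded a new diagnosis. Suppose a record exists but its last diagnostic entry dates from year 1. At the 5-year check, the only answer the extraction can return is that the diagnosis has not changed. The same answer comes back for a participant who died in year 2 without a recorded dementia, and for one seen last month and still classed as MCI. Only the last of these is a confirmed non-converter.

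If the three are pooled as controls, some controls are converters nobody recorded. That usually pulls the AUROC of a good marker down. If people with high marker values are kept under closer review, missed conversions concentrate among low values and the marker can look better than it is. The planned data would not show which had happened. Analysis wording added later could not fully repair this, because censoring and competing-risk methods need dates that nobody has been told to extract.

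**Working it through.** The protocol states no figure for conversion, loss of review or death, so there is nothing to reproduce. What follows is an illustration.

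**Inputs**
- True AUROC A = 0.88, the value the Background cites for NFL plus P-tau 181 against delayed verification of AD.
- True conversion p: not given; assumed 0.25 and 0.50.
- Share unreviewed m: not given; assumed 0.10, 0.20 and 0.30.
- All conversions among the unreviewed are missed, and these participants are labelled non-converters.

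**Loss unrelated to the marker**

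Share of true converters among labelled controls: q = p·m / (1 − p + p·m).

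A true converter compared with another true converter ranks higher half the time, so observed AUROC = (1 − q)·A + 0.5·q = 0.88 − 0.38·q.

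| p | m | q | Observed AUROC |
|---|---|---|---|
| 0.50 | 0.10 | 0.05/0.55 = 0.091 | 0.845 |
| 0.50 | 0.20 | 0.10/0.60 = 0.167 | 0.817 |
| 0.50 | 0.30 | 0.15/0.65 = 0.231 | 0.792 |
| 0.25 | 0.10 | 0.025/0.775 = 0.032 | 0.868 |
| 0.25 | 0.20 | 0.05/0.80 = 0.063 | 0.856 |
| 0.25 | 0.30 | 0.075/0.825 = 0.091 | 0.845 |

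**Some conversions recorded before the record stops**

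Someone diagnosed at year 3 and not seen at year 5 is still recorded as converted. If half the conversions among the unreviewed were caught this way, m in the formula is halved. At p = 0.50 the observed AUROC becomes 0.862, 0.845 and 0.830.

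**Review that depends on the marker**

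Binormal simulation with p = 0.50 and 30% unreviewed overall:

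| Reviewed above / below the marker median | True AUROC | Reported, unreviewed coded as non-converters |
|---|---|---|
| 90% / 50% | 0.80 | 0.824 |
| 90% / 50% | 0.88 | 0.878 |
| 50% / 90% | 0.80 | 0.63 |

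A second simulation used a true AUROC of 0.88, 20% overall loss and a logit slope of 1 per SD of the marker. Loss concentrated at high marker values gave 0.76 (30% conversion) or 0.71 (50% conversion). Loss concentrated at low values gave 0.888 or 0.883.

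**Leaving the unreviewed out**

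In that second simulation, dropping unreviewed participants gave 0.88 when loss was unrelated to the marker and 0.865 to 0.869 when it was related. Telling reviewed from unreviewed therefore removes most of the bias, but not all of it.

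**The case against.** The strongest reply is that the protocol contains no rule making an unreviewed participant a non-converter. That is right. A reader might infer that everyone lost, moved or dead is counted as a control, but the restriction to available records can equally mean that people without a usable record are left out. That would be selection, not misclassification. The misreading follows from the text only for a record that exists but stops early, or that ends with death.

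A reader might also infer a biased conversion proportion. No such estimate is among the listed analyses; conversion enters only through the AUROC and the regression.

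A third tempting reading is that volunteers recruited from outside would be followed elsewhere. The protocol does say "We plan to recruit through primary care and from public spaces using posters and leaflets", but that sentence belongs to Sub-Study 1, whose primary route is two studies run by the same group, with six further sources if those fall short. Item f) is listed under Substudy 2, whose participants have clinical CSF testing at the centre. The record check covers both sub-studies and is not limited to the centre's own records, so the recruitment argument is weak support.

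Censoring and competing-risk methods may properly sit in an analysis plan that is not shown. Someone who dies without dementia did not convert, so classing that person as a non-converter is one defensible definition. Progression is also a secondary objective (2.1.3.5) of a feasibility study. All this limits the weight of the point. What stands is that the extraction is specified in the protocol and omits the dates that any such method would need.

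**Conclusion.** The point holds as a gap in data collection and outcome definition. Followed as written, section 8.2 cannot separate no dementia at review from no review or from death, and item f) of section 10.2 takes that reading as its outcome.

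The size is conditional. For a true AUROC of 0.88, loss unrelated to the marker and every conversion among the unreviewed missed, the reported value would be about 0.85 to 0.79 at 50% conversion and 10-30% unreviewed, and about 0.87 to 0.85 at 25% conversion. The fall is smaller if some of those conversions were recorded earlier. With marker-related review the bias ranges from a slight rise through almost none to a large fall. The conversion and loss rates are assumptions, so the documents do not support a claim that the AUROC will be biased by a given amount or in a given direction. The change is worth making before the 2-year check, because it is cheap then and would need a second extraction later.

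**What to change.** At the planned record check, also extract three dates: the last documented cognitive or diagnostic review, any dementia diagnosis, and death. Say what makes a record available and how participants without one are handled.

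In sections 8.2 and 10.2 f), state that:
- a participant is a non-converter at a horizon only if a review within a pre-stated window around that horizon, or after it, records no dementia;
- otherwise follow-up is censored at the last documented review;
- death without dementia is a competing event.

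Analyse time to conversion, and use a time-dependent AUROC whose censoring weights condition on the baseline marker, since weights that ignore the marker would not deal with marker-related review. Report the proportion reviewed at each horizon by baseline marker status. The horizon also needs a stated origin for each participant, because the protocol says "In both substudies, the date will be measured from the date of the last participant's venepuncture", which leaves early recruits with longer elapsed time at each check.

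The cost is three dates per participant in an extraction already planned, some added wording, and somewhat wider intervals because fewer participants count as confirmed controls.

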#### 8.3 Source Data Documentation

For the purposes of this section, 'secure computers' describes computers accessible only to study investigators which are password protected and hosted on either the University of Bristol or North Bristol NHS Trust IT infrastructure. All source data stored electronically will be stored securely and will be accessible by investigators involved in collecting or analysing the data and third party organisations involved in maintaining the infrastructure for its collection (e.g. Brain Products UK). Source data refers to any raw, unprocessed data.

### 8.3 Case Report Forms

Source documents will be entered into a secure database comprising electronic Case Report Forms for all participants within 7 days of the source record being created.

#### 9 DATA MANAGEMENT

#### 9.1 Personal Data

The following personal data will be collected as part of the research:

- Name
- Address
- Telephone Number
- Email Address
- Date of Birth
- NHS Number

Personal data will be stored by the research team at the study site in a locked cabinet in the Bristol Brain Centre, North Bristol NHS Trust. This data will only be available to delegated members of the research team at site. The data will also be made available for monitoring or audit by the sponsor team if required. Personal data will be archived and stored securely in a locked filing cabinet on site for 3 years after the completion of the study, and then securely destroyed.

# 9.2 Storage

All source data stored electronically will be stored securely and this will be accessible by investigators involved in collecting or analysing the data. Participants will be informed that anonymised data may be shared with other approved reputable researchers utilising data management policies of the University of Bristol and the bris.ac.uk repository. This would

SleepAD Protocol v6.0 6th September 2024

require an appropriate Data Access Agreement and a Data Request Form. We will signpost to the opportunity for data sharing on our professional webpages.

### 9.2.1 Behavioural and participant data

Behavioural data stored on University of Bristol computers and servers will be pseudo-anonymised. Safety copies will be kept on encrypted hard-drives. The participants will be explicitly consented for the storage of their pseudo-anonymised data on University of Bristol computers in the consent form. Each participant's identity will be linked to their subject ID only on paper forms and in a log file, which will include participants' names, addresses and ID numbers. All identifiable paper records will be stored in secure locked cabinets. No identifiable information about the participant will leave the Bristol Brain Centre in any form. Any identifiable electronic information will be stored on NHS servers.

### 9.2.2 Sleep recordings

All raw study data relating to sleep recordings will be stored for a period of 20 years after publication as this is a quickly advancing field with the potential for new insights to afford new opportunities for analysis. To support future ethically-approved research, data may be shared anonymously with other bona fide researchers to support their work, and may be uploaded to the Dementia Platforms UK Data Portal (funded by the Medical Research Council).

### 9.2.3 Samples

Blood samples collected will be centrifuged and the plasma layer divided into 4 separate polypropylene tubes. They will initially be stored in the Bristol Brain Centre -70 freezer. One sample from each participant will be sent by courier to UCL laboratories for the main analysis. The remaining samples will be stored in Bristol Dementia Research Group freezers for future use within our group or by other bonafide researchers with appropriate research ethics and sample transfer agreements. A small sample from the remaining erthyrocyte layer will be transferred to a blood stain card and stored securely in the Bristol Dementia Research Group laboratory. In batches, DNA will be extracted from the blood stain cards and genotying will be performed using Taqman Assays (Applied Biosystems Assay-On-Demand part numbers C\_\_3084793\_20 and C\_\_904973\_10).

Where CSF is also being collected as part of routine clinical care, we will also send an extra sample (<5ml) to UCL, with the remainder stored in Bristol as above. CSF and blood will only be handled by clinical facilities and laboratories (Bristol Brain Centre, South West Dementia Brain Brank, and UCL) experienced in employing universal precautions to avoid contamination or spills.

#### 9.3 Confidentiality

Participant confidentiality will be respected at all times. Identifiable information may be shared with the participant's GP in line with patient consent.

#### 9.4 Public Release

SleepAD Protocol v6.0 6th September 2024

Any information that could identify individual participants will not be released into the public domain. Participants will be informed that anonymised data may be shared with other approved reputable researchers utilising data management policies of the University of Bristol and the bris.ac.uk repository. This would require an appropriate Data Access Agreement and a Data Request Form. We will signpost to the opportunity for data sharing on our professional webpages.

#### 9.5 Data Loss

The technology used in the study will be set up for each participant according to a rigorous protocol agreed by the research team, and participants are provided with written and verbal information on study activities to ensure adherence to protocol. However due to the remote and technology-focused nature of the study, it is possible for data to be lost or not collected due to technological issues (e.g., battery failures).

If a significant portion of data is missing on a given task, participants may be asked if they are willing to repeat an EEG night or blood test if appropriate within the 3 month study period. The participant can decline repeating any measures without this affecting their participation in the study. Similarly, if appropriate in the opinion of the Chief Investigator, participants may be asked to complete study activities outside of their main study period if study protocol has changed (and participants will be reconsented as appropriate).

### 10 STATISTICS AND DATA ANALYSIS

### 10.1 Sample Size Calculation

#### For substudy 1

Sample Size: of 50-100 allows key feasibility parameters to be estimated with a suitable level of precision

# For substudy 2

Sample Size: of 100 will allow key feasibility and diagnostic accuracy parameters to be estimated with a suitable level of precision e.g. a marginal error of 0.08 assuming an AUROC of 0.9 and 50% prevalence in binary classification of AD | not AD from biomarkers.

### 10.2 Proposed Analyses

#### For Substudy 1

Data analysis will:

- a) Quantify the proportion of missing data for sleep nights with high density EEG. Post hoc analysis will also explore whether any baseline questionnaire outcomes associate with poor data quality (larger levels of missing data)
- b) Calculate acceptability ratings for home EEG
- c) We will analyse non-REM duration from high density EEG and assess whether or not we can replicate the observed association between sleep metrics and memory observed from laboratory polysomnography, e.g. in the DOPAMIND study, when using home high density EEG.
- d) Quantify the proportion of datasets for sleep nights with pulse oximetry which are sufficiently complete to enable clinical screening for Obstructive Sleep Apnoea.

### For Substudy 2

Analysis of samples: will be on using the SIMOA platform for research use.

SleepAD Protocol v6.0 6th September 2024

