#### 2.1.2 Primary Objectives

### Theme 1

2.1.2.1 Feasibility of home high-density EEG (primary objective);

2.1.2.2 Acceptability of home EEG;

#### Theme 2

2.1.2.3 Feasibility of blood biomarkers for AD;

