### 2.2 Hypotheses

### 2.2.1 Primary Hypotheses:

### Theme 1

Home high-density EEG are feasible and acceptable in people with MCI and AD

### Theme 2

• Blood biomarkers are feasible and acceptable in people with MCI and AD.

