### 4.4 Participant Numbers

### For Sub-Study 1

Sample Size: of 50 allows key feasibility parameters to be estimated with a suitable level of precision

### For Sub-Study 2

Sample Size: of 100 will allow key feasibility and diagnostic accuracy parameters to be estimated with a suitable level of precision e.g. a marginal error of 0.08 assuming an AUROC of 0.9 and 50% prevalence in binary classification of AD | not AD.

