### 6.3 Main Study Assessments

#### For Substudy 1

- Venepuncture of 5-10 ml blood biomarkers taken for analysis of biomarkers (P-tau & NFL, GFAP and abeta42/40, and possibly others in future). The blood sample will either be arranged to be taken during a routine clinical appointment venepuncture at the Brain Centre (i.e. not an extra venepuncture), or during a separate appointment (which would require a new venepuncture).
- Sleep recording participants will undergo EEG recording at home for 3 nights and will also complete a Consensus Sleep Diary questionnaire [62] each night. The sleep monitoring will be performed using high-density at-home EEG equipment which will be set up by the researcher in the participant's home. This will involve participants undergoing full polysomnography (PSG), where electrophysiological data from electrodes placed on the scalp, face and body will be recorded. The home setup is designed to closely replicate the setup used in sleep laboratories. Participants will wear a 32-channel sleep cap including scalp and auxiliary channel location using a wireless LiveAmp 32-channel active electrode system (Brain Products UK). EEG recordings are acquired on an internal memory system and will subsequently be downloaded to a secure University of Bristol server. Although we do not currently have experience of sleep recordings in Alzheimer's disease, we have experience from recording sleep in patient populations of similar age, living with chronic pain. In our experience, these patients tolerate sleep recordings

SleepAD Protocol v6.0 6th September 2024

- well. Numerous EEG studies in Alzheimer's disease are reported in the literature, as reviewed elsewhere [63].
- Pulse oximetry participants will be asked to undergo two nights of overnight pulse oximetry (concurrent with EEG recording) during the 3 night window of sleep recordings. A pulse oximeter is a device routinely used in NHS practice to collect pulse oximetry data, and will be used in line with NHS protocols to monitor pulse and oxygen saturation levels and screen for obstructive sleep apnoea (OSA). Overnight pulse oximetry is an accepted and widely used screening tool for moderate to severe OSA [64]. Those with abnormal results will be offered referral to the Non-invasive Ventilation Clinic and their GP will be informed with the participant's consent.

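### Section 10.2 fixes the home-EEG feasibility measure per night, which does not show how many people can complete home EEG

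*Protocol*

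**What the plan says.** The Theme 1 primary hypothesis (Protocol 2.2.1) is about people: "Home high-density EEG are feasible and acceptable in people with MCI and AD". Section 6.2 adds that the baseline questionnaires should help to identify the patients in whom home EEG will be feasible in later trials.

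Section 6.3 sets the recording schedule: "participants will undergo EEG recording at home for 3 nights", with pulse oximetry on two of those nights.

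The sample size is in participants. Section 4.4 says that a sample "of 50 allows key feasibility parameters to be estimated with a suitable level of precision"; section 10.1 says "of 50-100 allows key feasibility parameters to be estimated with a suitable level of precision". Neither gives an expected proportion or a margin for Sub-Study 1.

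The only stated analysis of EEG feasibility is section 10.2 a): "Quantify the proportion of missing data for sleep nights with high density EEG". It continues: "Post hoc analysis will also explore whether any baseline questionnaire outcomes associate with poor data quality". Section 10.2 d) uses the same unit for oximetry: "Quantify the proportion of datasets for sleep nights with pulse oximetry which are sufficiently complete".

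Two other rules bear on the count. Section 9.5 allows an EEG night with substantial missing data to be repeated within the three-month study period. Section 11.4.1 says that anyone who withdraws or is withdrawn will be replaced. Neither says how these nights or people enter the feasibility figure.

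**The concern.** The question is asked of people and the measure is defined on nights. A person's nights share the same tolerance of the cap, skin, home and equipment, and someone who stops after the first night loses the later ones. Missing nights may therefore be concentrated in a few people or spread thinly over many, and one night-level proportion cannot tell these apart.

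A later trial would act differently on the two patterns. If a fifth of nights are missing because a fifth of people cannot do the recording at all, the trial must recruit more people or select them. If most people lose an occasional night, scheduling a spare night may be enough.

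Replacement and repeat nights widen the gap. If people who could not tolerate the EEG leave the denominator when they are replaced, or a repeated night stands in for a failed one, the night-level figure can look good while saying little about the people who were enrolled.

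**Working it through.** **Inputs.** Three EEG nights and two oximetry nights per participant (6.3). Sample of 50 (4.4) or 50-100 (10.1); 50 is used below unless stated. The protocol gives no expected missing rate, no within-person correlation (ICC) and no Sub-Study 1 margin, so there is no figure of its own to reproduce. A missing rate of 20% of nights and a range of ICCs are assumptions made here, and each night is simplified to usable or not usable.

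**Step 1: what a 20% night-level figure implies for people.**
- Independent nights: all three usable 0.8³ = 51.2%; none usable 0.2³ = 0.8%.
- All missing nights in the same people: all three 80%; none 20%.
- In between, a beta-binomial model with s = 1/ICC − 1, a = 0.8s and b = 0.2s gives P(all three) = a(a+1)(a+2) / [s(s+1)(s+2)], and P(none) is the same expression with b in place of a. At ICC 0.5, s = 1, so P(all three) = 0.8 × 1.8 × 2.8 / 6 = 67.2% and P(none) = 0.2 × 1.2 × 2.2 / 6 = 8.8%.

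| ICC (assumed) | All three nights | At least two | None |
|---|---|---|---|
| 0 | 51.2% | 89.6% | 0.8% |
| 0.3 | 61.4% | 83.6% | 5.0% |
| 0.5 | 67.2% | 81.6% | 8.8% |
| 0.7 | 72.5% | 80.5% | 13.1% |
| near 1 | 80.0% | 80.0% | 20.0% |

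Every row has the same 20% of nights missing. For 50 people, the number with all three nights runs from 0.512 × 50 = 25.6 to 0.8 × 50 = 40, and the number with none from 0.4 to 10. Clustering raises the share with all three nights but lowers the share with at least two, so the night-level figure does not even give a consistent direction.

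**Step 2: oximetry.** With an assumed 20% of oximetry nights inadequate, the share of people with at least one adequate night is 1 − 0.2² = 96% if nights are independent and 80% if fully clustered.

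**Step 3: precision of a night-level proportion, should an interval be given.** Half-width = 1.96 × √(0.2 × 0.8 × DE / 150), with design effect DE = 1 + 2 × ICC.
- Nights treated as independent (DE 1): ±6.4 points.
- ICC 0.2 (DE 1.4): ±7.6.
- ICC 0.5 (DE 2.0): ±9.1.
- ICC 0.7 (DE 2.4): ±9.9.

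**Step 4: precision of a participant-level proportion.** For a proportion of 20%, 1.96 × √(0.2 × 0.8 / 50) = ±11.1 points; with 100 participants, ±7.8. For a proportion near 50%, the half-width at 50 participants is 1.96 × √(0.25 / 50) = ±13.9.

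**The case against.** A reader might infer that the protocol counts three correlated nights as three separate pieces of evidence, so that its interval is too narrow and its questionnaire tests too liberal. The document does not support that. Section 10.2 a) names no interval, test, model or independence assumption, and the sample-size statement does not count 150 nights. Where everyone contributes three nights, clustering does not bias the night-level proportion; it affects only an interval, which the protocol does not state. Section 6.2 frames the questionnaire question by patient, and section 10.2 labels it post hoc. A variance method is normally left to an SAP, which is not shown.

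The other side can also say that section 10.2 a) speaks of missing data for nights, which could be a graded quantity computed per night or per person. Withdrawals are documented for each participant (5.5, 14.2.1), and acceptability (10.2 b) comes from a questionnaire answered once per participant. The 51% to 80% range joins two limiting cases, so it is not a forecast.

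These points remove any charge about false precision. They do not remove the unit problem. The protocol itself has chosen the quantity for its primary objective, and no reading of section 10.2 a) yields a stated count of people who complete. The limiting cases are enough to show that the chosen quantity does not determine the answer.

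**Conclusion.** The concern holds as a mismatch between the primary question, which is about people, and the stated measure, which is per night. At an assumed 20% of nights missing, the same reported result is compatible with 51% to 80% of people completing all three nights and 0.8% to 20% completing none, depending only on how the losses cluster. That range runs from independence to complete clustering within people. It rests on the assumed rate and on treating a night as usable or not; other rates move the ends, but the night-level figure still does not fix the participant result.

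The precision figures in step 3 are conditional: they show what would follow if an interval ignored clustering, and are not evidence that the protocol plans one. The change should be made, because it costs little and bears on the primary objective, but nothing here invalidates the design or the data to be collected.

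**What to change.** - **10.2 a), headline:** report the number and proportion of enrolled participants with 0, 1, 2 and 3 usable EEG nights, with an exact or Wilson 95% interval on participants. The full distribution avoids having to guess how many nights a later trial would need. What makes a night usable should be written down before the data are examined.
- **Denominator:** keep participants who withdraw and are replaced (11.4.1). Where their information has to be disposed of under that section, report how many there were.
- **Repeat nights (9.5):** count the originally scheduled nights for the headline and show repeat nights separately.
- **Night-level proportion:** retain as secondary. Any interval should allow for clustering by participant, for example with a cluster-robust, GEE or beta-binomial method.
- **Questionnaires:** relate each baseline score to one missing-data value per participant, such as the number of missing nights.
- **10.2 d):** report the proportion of participants with at least one oximetry night adequate for screening, beside the night-level figure.

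This is a wording change that needs no new data, visits or participants. The cost is a wider headline interval: about ±11 points at 50 participants for a 20% proportion. Because that width depends on the sample size, the 50 in section 4.4 and the 50-100 in section 10.1 should be reconciled at the same time.
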